10.4.5 ADHERENCE AND RETENTION ANALYSES

Adherence to the dosing schedule will be tracked with a dosing calendar that participants will fill out daily. This calendar will be assessed by the study staff at each visit.

10.4.6 BASELINE DESCRIPTIVE STATISTICS

Baseline statistics will be calculated using means (standard deviations) and numbers (percentages).

10.4.7 PLANNED INTERIM ANALYSES

10.4.7.1 SAFETY REVIEW

Phase Ib:

This arm will be halted when the MTD has been determined. The proposed safety endpoints will be monitored at each weekly visit. Participants will be formally queried for medication related side effects and will undergo an EKG at each visit, which will be assessed by a medical internist/anesthesiologist.

Phase II:

This arm will be halted if 20% of the population experiences a severe adverse event. This decision will be made at the discretion of the DSMB. Safety endpoints will be monitored at each of the 3 study visits (baseline, week 1, week 4). Participants will be formally queried for medication related side effects and will undergo a repeat EKG at the week 1 visit, which will be assessed by a medical internist/anesthesiologist.

10.4.7.2 EFFICACY REVIEW

No interim analysis will be performed in either arm of this trial.

10.4.8 ADDITIONAL SUB-GROUP ANALYSES

Phase Ib:

The primary safety endpoints will not be sub-divided by demographic characteristics.

Phase II:

The primary endpoint, SNOT22 score, analysis will not be sub-divided by demographic characteristics.

10.4.9 MULTIPLE COMPARISON/MULTIPLICITY

N/a

10.4.10 TABULATION OF INDIVIDUAL RESPONSE DATA

Individual participant data will be listed be listed by visit number. In Phase Ib visits will be numbered (1,2,3...) by how many visits the participant has before they reach the MTD. In Phase 2 visits will be listed (baseline, week 1, week 4) per the schedule of events.

10.4.11 EXPLORATORY ANALYSES

N/a

10.5 SAMPLE SIZE

The sample size for the Phase II arm was determined in consultation with [name] (biostatistician). It is based on the MCID for the SNOT-22 and the least suare means value for the SNOT-22 that was determined by the previous oral verapamil trial conducted by [name]. The new, combined MCID for the SNOT-22 was determined to be 15.9. The standard deviation for this trial is 24. This was calculated using the standard deviation of the oral verapamil trial (30) and an r^2 of 50%. With a significance level of 0.05, a standard deviation of 24, and 80% power, a sample size of 20 is needed to detect a difference of 15.9.

10.6 MEASURES TO MINIMIZE BIAS

10.6.1 ENROLLMENT/ RANDOMIZATION/ MASKING PROCEDURES

Participants will be enrolled in the MEEI Sinus Center. Eligible patients will be informed about the trial by their physician in the Sinus Center. If they express interest a member of the study staff will enroll them after passing through all inclusion and exclusion criteria. There will be no blinding or randomization in either phase of this trial.

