4.2.2 SECONDARY ENDPOINTS

Phase Ib:

Intermediate toxicity will be defined as: a heart rate of <50, an asymptomatic BP reduction >30% from baseline or SBP <90mmHg, an asymptomatic AMP reduction >30% from baseline or MAP<55, an asymptomatic DBP reduction >30% from baseline, and a Meltzer Compliance Grade >4.

Mild toxicity will be defined as a Meltzer Compliance Grade of 2-3.

Phase II:

The secondary outcomes of Phase II will be to determine the efficacy of Verapamil HCl at the MTD as measured by a subjective 10cm visual analog scale(VAS), Meltzer topical irrigation satisfaction and compliance scores, and the validated Lund-Kennedy nasal endoscopy score(LKS).

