7.3.3 FOLLOW-UP

Phase 1B:

Participants will asked to fill out a SNOT-22, VAS, , Satisfaction scale, and Compliance scale. Adherence to the treatment regimen will be evaluated. An endoscopy will be recorded and scored. A mucus sample will be collected from the nasal cavity with a small sponge. Participants will be evaluated for side-effects. An EKG will be taken. If no intermediate toxicity or DLT is experienced the participant will be moved up to the next dose. Participants will be asked to perform the initial irrigation of their next dose while being monitored for 1 hour by clinical monitoring equipment. After monitoring the patients will be given a second EKG. The irrigant will be collected. If no EKG abnormalities that are deemed unsafe by the study safety officer are detected during or after the initial irrigation the participants will be prescribed the rest of the verapamil rinse.

Phase 2:

During the Week 1 follow-up visit participants will asked to fill out a SNOT-22, VAS, , Satisscation scale, and Compliance scale. Adherence to the treatment regimen will be evaluated. Participants will be evaluated for side-effects. An EKG will be taken. An endoscopy will be recorded and scored.

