7.3.7 SCHEDULE OF EVENTS TABLE

4	Phase Ib			Phase II			
Procedures	Screening	Enrollment/ Baseline	Weekly/Final Follow-up	Screening	Enrollment/ Baseline	Follow-up (Day 7)	Final Visit (Day 28)
Informed Consent (IC)	X		-	х			
Intake Form (IF)	X	3	į	x		3	
Pregnancy Test (PT)	X			x			
SNOT-22	100	х	х		х	х	X
Visual Analog Scale (VAS)	3	х	x		х	х	X
Electrocardiogram (EKG)		х	х		x	x	
Heart Rate (HR)		х	х		х	х	X
Blood Pressure (BP)	ŝ.	x	x		x	x	х
Lund-Kennedy Score (LKS)		x	x		х	x	X
Nasal irrigation (NI)		х	х		х		х
Mucus sponge (MS)	ý.	x	х		x	- 3	х
Satisfaction Scale (SS)		d	x			Х	х
Compliance Scale (CS)			×			×	х
Side effects (SE)			x			х	X

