10 STATISTICAL CONSIDERATIONS

10.1 STATISTICAL AND ANALYTICAL PLANS

All statistical analyses will be performed in conjunction with the consultant biostatistician([name]). The proposed sample size of 20 subjects for the Phase II expansion cohort was determined to detect, with an 80% power at a 5% type-1 error rate, a change of 15.9 points on the primary endpoint (ie. SNOT-22 score) between baseline and 4 weeks. This calculation was based on two assumptions. The first is a target effect size of 15.9 which represents a conservative value derived from the established MCID for the SNOT-22 of 8.9[65] and the LSM change in SNOT-22 of 27.7 derived from our previous trial of oral Verapamil(Section R.4.d)[19]. The second is an anticipated standard deviation of 24 which is calculated from the standard deviations of 30 both at the baseline and 8 week time point observed in our oral Verapamil trial and an r2 of 50% between the two time points. With a significance level of 0.05, a standard deviation of 24, and 80% power, a sample size of 20 would be needed to detect a difference of 15.9. Analysis of efficacy will be based on an intention-to-treat population that will include all enrolled patients. A mixed-effect model with repeated measures approach will be used to independently analyze the change in the SNOT-22, VAS, and LKS. An intraclass correlation coefficient (ICC) will be calculated to assess inter-rater agreement with respect to the LKS scores. Descriptive statistics will be used for demographics, baseline characteristics, and safety variables. Linear regression models will be fitted to examine the interaction effect between baseline characteristics, whole mucus and exosomal P-gp concentrations, mucus and irrigant cytokine concentrations, and treatment on change in SNOT-22 while adjusting for the baseline SNOT-22 score. Statistical analyses will be performed using the statistical software SAS (SAS Institute Inc., Cary, NC)

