10.2 STATISTICAL HYPOTHESES

- Primary Efficacy Endpoints: SNOT-22
 - H₀: There is no means difference between baseline SNOT-22 scores and 4 week SNOT-22 scores
- Secondary Efficacy Endpoints: VAS and LKS
 - o H₀: There is no means difference between baseline VAS scores and 4 week VAS scores
 - o H₀: There is no means difference between baseline LKS scores and 4 week LKS scores

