11 SOURCE DOCUMENTS AND ACCESS TO SOURCE DATA/DOCUMENTS

A Case Report Form (CRF) will be completed for each subject enrolled into the clinical study. The PI and/or their designee will review, approve and sign/date each completed CRF; the PI and/or designee's signature serving as attestation of the PI's responsibility for ensuring that all clinical and laboratory data entered on the CRF are complete, accurate and authentic. Source Data are the clinical findings and observations, test data, and other information contained in Source Documents. Source Documents are the original records (and certified copies of original records); including, but not limited to, hospital medical records, physician or office charts, physician or nursing notes, subject diaries or evaluation checklists, pharmacy dispensing records, and recorded data from automated instruments. When applicable, information recorded on the CRF shall match the Source Data recorded on the Source Documents. The EKG findings, SNOT-22, VAS, Side Effects, LKS, satisfaction, and compliance data will be recorded on the CRF which will serve as the primary source data for these data elements. Each form will be recorded in a study chart which is linked to the subject's study ID number. An electronic image capture system will be used to record nasal endoscopy which will be maintained on an encrypted MEEI server.

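### Phase II Lund-Kennedy scores: nothing masks the raters to visit, although the endoscopies are stored and could be read in random order at little cost

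*Combined protocol and SAP*

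**What the plan says.** - **Role of LKS.** Section 4.2.2 lists LKS among the Phase II secondary outcomes. Section 10.2 gives it its own null hypothesis: "There is no means difference between baseline LKS scores and 4 week LKS scores".
- **When it is scored.** Sections 7.3.2 (baseline), 7.3.3 (week 1) and 7.3.4 (week 4) each state for Phase II: "An endoscopy will be recorded and scored". The table in 7.3.7 marks LKS at the same three visits.
- **What is kept.** Section 11: "An electronic image capture system will be used to record nasal endoscopy which will be maintained on an encrypted MEEI server". The same section lists LKS among the items entered on the CRF, "which will serve as the primary source data for these data elements".
- **Who scores.** Section 10.1: "An intraclass correlation coefficient (ICC) will be calculated to assess inter-rater agreement with respect to the LKS scores". Agreement between raters needs at least two of them. The number is not given.
- **Masking.** Section 10.6.1: "There will be no blinding or randomization in either phase of this trial". Sections 10.6.2 and 10.6.3 are marked not applicable. No section removes visit labels or randomizes the reading order.
- **Not stated.** The Phase II text does not say whether LKS is scored live or from the stored recording. Section 4.1 links the recording to LKS grading, but under Phase Ib.

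**The concern.** LKS is the Phase II efficacy measure that staff score from an image, so it could be protected from expectation even though everyone knows the treatment. As the plan stands, a rater may know that one endoscopy precedes treatment and another follows four weeks of it. If that knowledge moves the scores, even slightly, the movement enters the estimated change in full, because there is no control arm to subtract it. The planned agreement coefficient looks like a safeguard, but it measures whether raters agree with one another. It does not show whether they lean the same way. At stake is whether a change in LKS can be read as a change in the endoscopic findings.

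**Working it through.** **1. The plan's own figure, to confirm the test.** Inputs from 10.1 and 10.5: difference 15.9, SD of change 24, alpha 0.05, power 80%, N = 20. For a paired t-test with 19 degrees of freedom, the two-sided critical value is 2.093 and the noncentrality is (15.9/24) × √20 = 2.963. Power is 0.802, against 0.780 at N = 19. The stated N of 20 therefore reproduces as a two-sided paired t-test on the change. It concerns SNOT-22 and is not in question. It shows which test and sample size to carry over to LKS.

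**2. Why a visit-linked shift cannot be identified.** Let D be the true mean LKS change and b the average amount by which raters score a post-treatment recording differently because they know it is post-treatment. The observed mean change estimates D + b. With one arm tested against zero, no contrast in the data isolates b.

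**3. Why the agreement coefficient does not reveal it.** Take week 4, with n participants and k raters. A two-way single-rater coefficient is (MSR − MSE) / (MSR + (k − 1)MSE + k(MSC − MSE)/n), where MSR, MSC and MSE are the mean squares for participants, raters and residual. Add a constant b to every score from every rater. Participant means, rater means and the grand mean all move by b, so every deviation and every mean square is unchanged. The week-4 coefficient is the same with or without the shift. The plan does not name the form of coefficient, but the argument holds for any form built from these mean squares.

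**4. Illustration of size.** The documents give no SD for LKS, so the shift is expressed as d = b divided by the SD of the paired change. The values of d are assumed. With no true effect, N = 20 and a two-sided 5% test, the chance of a significant result is the noncentral t tail probability with 19 degrees of freedom and noncentrality d × √20:

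| Assumed d | d × √20 | Chance of p < 0.05 |
|---|---|---|
| 0 | 0 | 0.050 |
| 0.1 | 0.447 | 0.071 |
| 0.2 | 0.894 | 0.136 |
| 0.3 | 1.342 | 0.247 |
| 0.5 | 2.236 | 0.5645 |

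The calculation takes the shift as constant across participants and uses a paired t-test as a simple stand-in. Section 10.1 names a repeated-measures mixed model and 10.4.2 a t-test or rank test. Steps 2 and 3 do not depend on that choice.

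**The case against.** **The trial is openly unblinded.** Section 10.6.1 says so plainly, and an open-label single-arm phase II study is a legitimate design. This stands to the extent that the absence of masked reading is neither an error nor a contradiction. But open-label dosing does not require readers to know the visit, and the material for masked reading is already collected.

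**The size is assumed.** Nothing in the documents supports any particular reader shift. This also stands, and the table is an illustration only.

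**The gain is limited.** After masking, placebo response, the effect of rinsing and natural course would still be mixed with any drug effect on LKS. This is correct. Masking removes one source of bias.

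**Stronger readings that the documents do not support.**

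- A reader might infer that several raters are known to read the Phase II recordings with the visit visible. The documents imply at least two raters, but not whether each scores every visit, nor whether they work live or from files.
- A reader might infer that LKS is biased in favor of the drug. Expectation of improvement would push that way, but Phase II entry also caps the Lund-Kennedy polyp score below 4 (section 5.1). Selecting low scores could pull that component the other way, so no net direction can be claimed.
- A reader might infer that the plan fails to say which SNOT-22 score qualifies a participant. Section 5.1 names the baseline score, and 7.3.2 and 7.3.7 place the only scheduled pre-treatment SNOT-22 at Enrollment/Baseline. What remains is a timing mismatch: 7.3.1 has all criteria reviewed at screening, where no SNOT-22 is scheduled.

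**Conclusion.** The point holds as a low-cost improvement to one secondary endpoint. The plan tests LKS change in a single arm, stores the recordings and implies more than one rater, yet specifies no masking to visit. The inability to separate a reader shift from a drug effect, and the blindness of the agreement coefficient to a shared shift, follow from the design without numerical assumptions. The false-positive rates of about 7% to 56%, against a nominal 5%, depend on assumed shifts of 0.1 to 0.5 SD, constant across participants and shared by raters. The sample size and the SNOT-22 primary analysis are unaffected.

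**What to change.** State in 10.6.1 that the raters already planned for the agreement analysis will score the stored Phase II recordings in random order, with visit and date removed, and that this masked score is the LKS value analyzed. Live scoring for eligibility stays as it is. State also that the agreement coefficient is computed on the masked scores.

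Costs:

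- Coding and shuffling about 60 recordings (20 participants × 3 visits), plus those of replaced participants. Coded participant numbers already exist (section 13.4).
- Scores become available after the visit instead of at it.
- Extra rater time if Phase II scoring was to be live.
- A separate CRF field for the masked score, because section 11 makes the CRF the primary source for LKS.

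No visit or patient procedure is added. Separately, as an editorial matter, reconcile the timing of the SNOT-22 eligibility check between 7.3.1 and sections 5.1, 7.3.2 and 7.3.7.

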10.6.2 EVALUATION OF SUCCESS OF BLINDING

N/a

10.6.3 BREAKING THE STUDY BLIND/PARTICIPANT CODE

N/a

11 SOURCE DOCUMENTS AND ACCESS TO SOURCE DATA/DOCUMENTS

A Case Report Form (CRF) will be completed for each subject enrolled into the clinical study. The PI and/or their designee will review, approve and sign/date each completed CRF; the PI and/or designee's signature serving as attestation of the PI's responsibility for ensuring that all clinical and laboratory data entered on the CRF are complete, accurate and authentic. Source Data are the clinical findings and observations, test data, and other information contained in Source Documents. Source Documents are the original records (and certified copies of original records); including, but not limited to, hospital medical records, physician or office charts, physician or nursing notes, subject diaries or evaluation checklists, pharmacy dispensing records, and recorded data from automated instruments. When applicable, information recorded on the CRF shall match the Source Data recorded on the Source Documents. The EKG findings, SNOT-22, VAS, Side Effects, LKS, satisfaction, and compliance data will be recorded on the CRF which will serve as the primary source data for these data elements. Each form will be recorded in a study chart which is linked to the subject's study ID number. An electronic image capture system will be used to record nasal endoscopy which will be maintained on an encrypted MEEI server.

12 QUALITY ASSURANCE AND QUALITY CONTROL

The PI and DSMB will verify that the study is conducted and data are generated, documented, and reported in compliance with the protocol, GCP, and the applicable regulatory requirements (e.g. FDA, Clinicaltrials.gov). The PI and study staff will provide direct access to all source data/documents and reports for the purpose of monitoring and auditing by the DSMB, and inspection by local and regulatory authorities.

13 ETHICS/PROTECTION OF HUMAN SUBJECTS

13.1 ETHICAL STANDARD

The PI will ensure that this study is conducted in full conformity with Regulations for the Protection of Human Subjects of Research codified in 45 CFR Part 46, 21 CFR Part 50, 21 CFR Part 56, and/or the ICH E6.

13.2 INSTITUTIONAL REVIEW BOARD

The protocol, informed consent form(s), recruitment materials, and all participant materials will be submitted to the IRB for review and approval. Approval of both the protocol and the consent form must be obtained before any participant is enrolled. Any amendment to the protocol will require review and approval by the IRB before the changes are implemented to the study. All changes to the consent form will be IRB approved; a determination will be made regarding whether previously consented participatns need to be re-consented.

13.3 INFORMED CONSENT PROCESS

13.3.1 CONSENT/ASSENT AND OTHER INFORMATIONAL DOCUMENTS PROVIDED TO PARTICIPANTS

Consent forms describing in detail the study agent, study procedures, and risks are given to the participants and written documentation of informed consent is required prior to starting administering the study drug. The following materials are submitted with this protocol:

- Informed consent form
- Informed consent script

13.3.2 CONSENT PROCEDURES AND DOCUMENTATION

Extensive discussion of risks and possible benefits of participation will be provided to the participants and their families. Consent forms will be IRB-approved and the participant will be asked to read and review the document. The PI and/or designee will explain the research study to the participant and answer any questions that may arise. All participants will receive a verbal explanation in terms suited to their comprehension of the purposes, procedures, and potential risks of the study and of their rights as research participants. Participants will have the opportunity to carefully review the written consent form and ask questions prior to signing. The participants will have the opportunity to discuss the study with their surrogates or think about it prior to agreeing to participate. The participant will sign the informed consent document prior to any procedures being done specifically for the study. The participants may withdraw consent at any time throughout the course of the trial. A copy of the informed consent document will be given to the participants for their records. The rights and welfare of the participants will be protected by emphasizing to them that the quality of their medical care will not be adversely affected if they decline to participate in this study.

13.4 PARTICIPANT AND DATA CONFIDENTIALITY

Participant confidentiality is strictly held in trust by the participating investigators and their staff. This confidentiality is extended to cover testing of biological samples in addition to the clinical information relating to participants. Therefore, the study protocol, documentation, data, and all other information generated will be held

in strict confidence. Participants will be linked to their information with a coded identification number. No information concerning the study or the data will be released to any unauthorized third party without prior written approval of the PI.

The DSMB, representatives of the IRB or any other regulatory agency may inspect all documents and records required to be maintained by the investigator, including but not limited to, medical records (office, clinic, or hospital) and pharmacy records for the participants in this study. The clinical study site will permit access to such records.

The study participant's contact information will be securely stored at the clinical site for internal use during the study. At the end of the study, all records will continue to be kept in a secure location for as long a period as dictated by local IRB and Institutional regulations.

13.4.1 RESEARCH USE OF STORED HUMAN SAMPLES, SPECIMENS OR DATA

Samples and data collected under this protocol may be used to study CRSwNP. No genetic testing will be performed.

Access to stored samples to be limited using a locked freezer at MEEI. Samples and data will be stored using codes assigned by the PI. Data will be kept in password-protected computers. Only the PI and study staff will have access to the samples and data. Study participants who request destruction of samples will be notified of compliance with such request and all supporting details will be maintained.

13.5 FUTURE USE OF STORED SPECIMENS

Data collected for this study will be analyzed and stored at MEEI. Samples stored for this study will not be used for future research projects.

14 DATA HANDLING AND RECORD KEEPING

14.1 DATA COLLECTION AND MANAGEMENT RESPONSIBILITIES

Data collection is the responsibility of the clinical trial staff under the supervision of the PI. The investigator is responsible for ensuring the accuracy, completeness, legibility, and timeliness of the data reported.

All source documents should be completed in a neat, legible manner to ensure accurate interpretation of data. Black ink is required to ensure clarity of reproduced copies. When making changes or corrections, cross out the original entry with a single line, and initial and date the change. DO NOT ERASE, OVERWRITE, OR USE CORRECTION FLUID OR TAPE ON THE ORIGINAL.

